3.1.2 Study Intervention Phase

Intervention will occur during the patient's previously scheduled office visit. The patient will be seen by the PI for the originally scheduled consultation. After the initial consultation, proper screening, and informed consent of the patient is completed the patient will answer one survey and undergo 3-D photography and standard digital photography. After injections the patient will have photographs and the survey administered again before the initial visit is complete.

3.1.3 Follow Up Phase

The follow-up phase of a patient is approximately 90 ± 7 days. Follow-up will begin after treatment is administered. Required visits occur at 14 ± 3 days, 28 ± 3 days and 90 ± 7 days. At each required follow-up visit one questionnaire will be administered, the FACE-Q in addition to the 3-D Vectra imaging.

3.1.4 Primary Study Endpoints

The primary endpoint will be to quantify patient satisfaction with minimally invasive volume correction.

- Determine patient reported outcomes and satisfaction with the validated survey FACE-Q
- Determine the volumetric changes at each time point up to 90 days

3.1.5 Secondary Study Endpoints

- Correlate degree of patient satisfaction with volumetric measurements from 3-D analysis after treatment over the 90 day period

4 Study Population and Duration of Participation

4.1 Inclusion Criteria

- *Female patients 40 – 65 years of age*

4.2 Exclusion Criteria

- *Male patients*
- *Prior surgical facial rejuvenation procedures*
 - *Facelift*
 - *Neck lift*
 - *Blepharoplasty*
 - *Facial fat grafting*
- *Prior minimally invasive rejuvenation procedure ≤ 12 months*
- *Known contraindications to devices or drugs used in this study*

CONFIDENTIAL

This material is the property of the University of Pennsylvania.

- *Facial paralysis*
- *Congenital facial asymmetry*
- *Pregnant women*
- *Patient actively taking blood thinners*

4.3 Subject Recruitment

Eligible subjects will be identified from principal investigator's clinic schedule and recruited from local area including employees. Potential subjects will be screened by a member of the study team for eligibility, using the electronic medical record (EMR), according to the inclusion and exclusion criteria listed above. In clinic, the principal investigator will introduce the study to eligible patients. A member of the study team will give a written informed consent, and will answer any questions the patients may have. Eligible patients may be contacted at home through a phone call by a member of the study team to introduce the study to assess interest in participation. A member of the study team will answer any questions the patients may have before and after the informed consent is signed. The informed consent process will be documented in the subject's medical record or comparable source document.

4.4 Duration of Study Participation

Subject participation will begin during the office when the informed consent is signed. Once the patient is confirmed to be a study candidate by the participating physician, they can be enrolled. Patients will be asked to return for 3 follow-up visits over the next 90 ± 7 days.

4.5 Total Number of Subjects and Sites

Total accrual will be 100 patients. The aim will be to enroll all subjects at the University of Pennsylvania Health System (UPHS).

5 Study Intervention

The initial consultation by the principal investigator will determine the injection area and the volume of the injections. Injections of the fillers will be used according to the FDA approval indicated use. All three areas will be injected (nasolabial folds, marionette lines, and lips).

Restylane-L® used for the nasolabial folds and/or marionette lines up to a total of 4 cc (2 cc/side).
Restylane-L® Lyft used for severe nasolabial folds and or marionette lines up to a total of 2 cc (1 cc/side)
Restylane-L® Lyft used for malar deflation will receive up to a total of 4 cc of (2 cc/side)
Restylane® Silk in the lips and cutaneous vermillion used for perioral volume loss will receive up to 1cc per lip.

5.1 Description

Restylane-L® is indicated for mid-to-deep dermal implantation for moderate to severe facial wrinkles and folds, such as nasolabial folds. It is indicated for submucosal implantation for lip augmentation in patients over the age of 21. Restylane-L® consists of stabilized, hyaluronic acid (HA) generated by streptococcal bacteria and formulated to a concentration of 20 mg/ml, suspended in physiological buffer of pH7 with 0.3% lidocaine. Restylane-L® is a transparent viscous and sterile gel, supplied in disposable glass syringes contain 0.4 or 0.7 ml gel.

Restylane-L® Lyft is indicated for implantation into the deep dermis to superficial subcutis for the correction of severe facial folds and wrinkles, such as nasolabial folds and for subcutaneous to supraperiostal implantation for check augmentation correction of age-related midface contour deficiencies in patients >21 years of age. Restylane-L® Lyft is a sterile gel of stabilized hyaluronic acid generated by staphylococcus species of bacteria, suspended in phosphate buffer saline at pH 7 at a concentration of 20 mg/ml with 0.3% lidocaine.

Restylane® Silk is indicated for submucosal implantation for lip augmentation and dermal implantation for correction of perioral rhytids in patients >21 years of age. Restylane® Silk is a gel of hyaluronic acid generated by streptococcus species of bacteria stabilized and suspended in phosphate buffered saline at pH 7 at a concentration of 20 mg/ml with 0.3%.

CONFIDENTIAL

This material is the property of the University of Pennsylvania.

5.2 Intervention Regimen

5.2.1 Study Group

The patient will receive the injections of the fillers in all three areas the nasolabial folds, marionette lines, and lips as recommended by the PI during the initial consultation of the regularly scheduled appointment.

5.3 Receipt

Galaderma the manufacturer of Restylane-L®, Restylane-L® Lyft, and Restylane® Silk, will provide the fillers for the study. The products will be shipped directly to the PI and stored in a drug labeled refrigerator. The products will be inventoried when they arrive and designated as used per patient.

5.4 Storage

The products will be shipped directly to the PI and stored in a drug labeled refrigerator in the PI's office. Restylane-L®, Restylane-L® Lyft and Restylane® Silk must be used prior to expiration date printed on the package and stored at a temperature $\leq 77^{\circ}\text{ F} \geq 36^{\circ}\text{F}$, protected from sunlight. Do NOT freeze.

5.5 Preparation and Packaging

Restylane-L®, Restylane-L® Lyft and Restylane® Silk come prepared in sterile disposable glass syringes with luer-lock fitting. Restylane products are co-packed with sterilized needles (needle gauge specified on package). Sterile syringes will be used for each vial assigned to each subject.

5.6 Administration and Accountability

Restylane® products come supplied with a patient record label as a part of the syringe label. Remove it by pulling the flap marked with three small arrows. This label is to be attached to patient records to ensure traceability of the product. The extra label will also be placed on the device accountability log.

5.7 Return or Destruction of Investigational Product

The unused products will be disposed in the fashion of biohazard material.

6 Study Procedures

TABLE 4 SCHEDULE OF STUDY PROCEDURES

| | Baseline Visit | Intervention | Follow-up Visit 1 Day 14 | Follow-up Visit 2 Day 28 | Follow-up Visit 3 Day 90 |
|--------------------|----------------|--------------|-----------------------------|-----------------------------|-----------------------------|
| Visit Window | Day 1 | Day 1 | Day 14 ± 3 | Day 28 ± 3 | Day 90 ± 7 |
| Eligibility | X | | | | |
| Informed Consent | X | | | | |
| Demographic | X | | | | |
| Medical History | X | | | | |
| Consultation | X | | | | |
| Vectra Photography | | X | X | X | X |
| FACE-Q | | X | X | X | X |
| Adverse Events | X | X | X | X | X |

CONFIDENTIAL

This material is the property of the University of Pennsylvania.

6.1 Study Intervention Phase

6.1.1 Screening/Baseline Visit (Day 1)

Electronic medical records from the most recent office visit will be used to initially screen according to the inclusion/exclusion criteria in Section 4.1 and 4.2. The current office visit will be used to confirm the patient's eligibility, if confirmed the patient will be approached to consent to participate in the study. When the patient is consented the screening/baseline documentation will take place. The screening and baseline data collection will include demographic information, medical history, and surgical history. The screening and baseline visit and intervention can occur in the same office visit.

- Medical Record Review**

Variables abstracted from the electronic medical record

- Date of Birth
- Height
- Weight
- Race
- Gender
- Any history of disease
- Surgical facial rejuvenation history

- Consultation**

The patient will undergo the initial consultation with the PI. The consultation will be documented in the patient's EMR.

6.1.2 Intervention (Day 1)

- If patient is concerned of child bearing potential, a urine pregnancy test will be administered.
- FACE-Q survey will be administered prior to injections
- Photographs with the Vectra 3D camera will be administered prior to injections
- Injections
 - The patient will receive the fillers injectors as suggested in the consultation in all three areas of the face.
- Photographs with the Vectra 3D camera will be administered 30 minutes after injections

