11.1 Risks

All treatments used in this protocol will be used according to the FDA approved intended use. No unexpected risks should occur. Risks that may be experienced from any injection are swelling bruising, redness, itching, infection, or pain.

All HA containing products have the risk of potential tissue loss if there is unrecognized intravascular injection of the fillers. All HA fillers are dissolvable and if you are strongly dissatisfied with the treatment filler or if there is evidence of tissue threat, HA can be removed with hyaluronidase (Vitrase)®. Restylane Silk carries an extra risk of hyperpigmentation to the risks from injection listed above. A risk related to all injectables used in this study is unevenness or lumps.

CONFIDENTIAL

This material is the property of the University of Pennsylvania.

Reproductive risks: If patient is of child-bearing potential, a urine pregnancy test may be administered prior to injection to confirm negative pregnancy status. The effects of this drug/device, there could be serious harm to unborn children or children who are breast-feeding. These effects could also harm the mother.

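### The Day 1 pregnancy-test rule is garbled in 6.1.2 and only permissive in 11.1, and the breast-feeding warning in 11.1 has no named exclusion to match it

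*Combined protocol and SAP*

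**What the plan says.** Section 4.1 admits "Female patients 40 – 65 years of age". Section 4.2 and the Study Summary both exclude "Pregnant women", and both carry the general item "Known contraindications to devices or drugs used in this study". Neither list mentions breast-feeding or lactation.

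Two places deal with the pregnancy test:

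- Section 6.1.2, the Day 1 procedure list, has as its first item: "If patient is concerned of child bearing potential, a urine pregnancy test will be administered".
- Section 11.1, the risk description in the ethics chapter, says: "If patient is of child-bearing potential, a urine pregnancy test may be administered prior to injection to confirm negative pregnancy status".

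The same paragraph of 11.1 then warns that "there could be serious harm to unborn children or children who are breast-feeding".

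The schedule in section 6, headed "TABLE 4 SCHEDULE OF STUDY PROCEDURES", has no row for a pregnancy test.

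**The concern.** A test that enforces a stated exclusion should be triggered by something staff can determine, and its status as required or optional should be the same wherever it appears. Here the section that requires the test has an unclear trigger, and the section with a clear trigger does not require the test. Staff who take 6.1.2 at its word, or who work from 11.1, could inject a woman of child-bearing potential without testing her and still be following a sentence of the protocol.

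The breast-feeding point is of a different kind. The protocol names a serious risk to a group and then does not name that group among those excluded. The same sentence of 11.1 puts unborn and breast-fed children side by side, but only pregnancy is carried into the exclusion lists. On the named criteria, a breast-feeding woman can enrol.

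What is at stake is participant safety on a small scale. The trial's statistical conclusions are not involved.

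**Working it through.** The point is about wording, so the check is to set the sections against each other. The plan states no figure to reproduce.

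**Step 1: the two test rules under each reading of the trigger.**

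| Reading of 6.1.2 | What 6.1.2 requires | What 11.1 adds | Result for a woman of child-bearing potential |
|---|---|---|---|
| Literal: the patient is worried | Test only if she is worried | Test allowed, not required | If she is not worried, no sentence requires a test |
| Slip corrected: the patient is considered to be of child-bearing potential | Test for every such woman | Test allowed, not required | Testing satisfies both sections; omitting the test satisfies 11.1 but breaches 6.1.2 |

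Correcting the slip removes most of the problem but leaves *will* in one section and *may* in the other.

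**Step 2: whether anything else settles it.** Table 4 lists eight procedures: eligibility, informed consent, demographics, medical history, consultation, Vectra photography, FACE-Q and adverse events. None is a pregnancy test. The record variables listed in section 6.1.1 do not name pregnancy, menopausal or breast-feeding status. Section 6.1.1 also allows screening, baseline and intervention in one office visit, so the Day 1 test may be the only objective check before injection.

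**Step 3: what follows a positive test.** Section 4.2 excludes pregnant women, and 11.1 gives the purpose of the test as confirming that the patient is not pregnant. A positive result therefore already bars injection. The gap is only whether the test is done.

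**Step 4: whether the general exclusion covers breast-feeding.** It would do so if breast-feeding were a contraindication to one of the three fillers. Section 5.1 describes the products through their indications and minimum age, for example "It is indicated for submucosal implantation for lip augmentation in patients over the age of 21", and lists no contraindications. The documents leave the question open.

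**Step 5: upper bound on the cost.** Total accrual is 100 (section 4.5), and 6.1.2 places the test once, on Day 1. The most tests that could be needed is 100 × 1 = 100. The true number is lower to the extent that women in this age range are not of child-bearing potential; the documents do not give that share.

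**The case against.** The strongest reply is that 6.1.2 governs. It is the list staff work through on Day 1, and the test comes first on it, ahead of the questionnaire, the photographs and the injections. Section 11.1 is a risk narrative, parts of which address the reader directly as a consent form would. A permissive verb there does not cancel an instruction in the procedures, and 11.1 itself supplies the trigger that 6.1.2 evidently meant. Table 4 is weak evidence either way, since it is coarse enough to have no row for the injections themselves. Pregnancy is also screened by other means: eligibility is checked from the record and confirmed at the visit (6.1.1), and a physician confirms candidacy before enrolment (4.4).

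Most of this stands. It makes the test conflict mainly a drafting fault. It does not repair the trigger, which is in the governing section itself.

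On breast-feeding, the reply is that the product labelling is not part of these documents, that the warning is a broken sentence tied to no particular filler, and that the general contraindication item may already cover the case. This is fair as far as it goes. It means one cannot say whether the exclusion is missing or the warning is misplaced. One of the two still needs attention, unless the sponsor can show that the general item applies.

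A reader might infer three stronger things that the documents do not support:

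- That the protocol makes pregnancy testing optional, or lets pregnant women be injected. The procedure section uses *will*, and pregnancy is a named exclusion.
- That these fillers are known to harm breast-fed children. The only basis is the general warning in 11.1, and no contraindication is given for any product.
- That the number of women left untested can be estimated. The documents give neither an age distribution within 40 to 65 nor the share of child-bearing potential. Any such count would rest on assumed ages and cut-offs, and would describe women to whom the rule applies rather than women missed or harmed.

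**Conclusion.** The point holds as a minor safety and consistency finding with two parts. First, the required test in 6.1.2 rests on a garbled trigger, and 11.1 weakens it to an option. Staff would ordinarily follow 6.1.2 and read the trigger sensibly, so the practical risk is that an occasional woman of child-bearing potential goes untested, not that testing is absent. Second, breast-feeding is warned about but not named as an exclusion, and the documents do not show that the general item fills the gap.

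The safety gain from correction is small. That judgement assumes that the record review and the physician's confirmation work as described, and that breast-feeding is uncommon between 40 and 65; the documents give no figure for the latter. No endpoint, sample size or analysis depends on the outcome. The change is worth making because it is cheap and concerns a step that protects participants.

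**What to change.** Use the same sentence in 6.1.2 and 11.1, for example: *For every woman of child-bearing potential, a urine pregnancy test will be done before injection; injection goes ahead only if the result is negative.* The last clause only makes explicit what 4.2 and the stated purpose of the test already imply.

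Add breast-feeding women to the exclusions in 4.2 and the Study Summary. If the sponsor confirms that the warning does not apply to these products, correct 11.1 instead.

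A row in Table 4 and a baseline item recording child-bearing and breast-feeding status would help but are optional.

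The cost is a short wording amendment and at most 100 urine tests in total, most of which 6.1.2 already provides for. If breast-feeding becomes an exclusion, there may be a very small loss of eligible women.

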6.2 Follow Up Phase of the Study

6.2.1 Follow-up Visits

- **Visit 1 (Day 14 ± 3)**
 - Photographs with the Vectra 3D camera
 - FACE-Q will be administered
- **Visit 2 (Day 28 ± 3)**
 - Photographs with the Vectra 3D camera
 - FACE-Q will be administered
- **Visit 3 (Day 90 ± 7)**
 - Photographs with the Vectra 3D camera
 - FACE-Q will be administered

CONFIDENTIAL

This material is the property of the University of Pennsylvania.

6.3 Unscheduled Visits

An unscheduled visit or extra visit will be defined as a visit scheduled outside of the protocol due to any concern of the patient's treatment related to the injections. If an unscheduled visit occurs, it is preferred to collect the information during the visit for example any adverse event. If an unscheduled visit is missed a follow-up phone interview is adequate if more information is required than is available in the patient's EMR.

6.4 Subject Withdrawal

Subjects may withdraw from the study at any time without impact to their care. The Investigator may also withdraw subjects who violate the study plan, or to protect the subject for reasons of safety or for administrative reasons. It will be documented whether or not each subject completes the clinical study.

6.4.1 Data Collection and Follow-up for Withdrawn Subjects

Subjects who withdraw consent to participate in the study may be asked for one final visit or phone interview to collect any study endpoints or adverse events at that time.

6.5 Early Termination Visits

If a subject decides to leave the study early or is asked by the investigator to cease participation in the study the subject's participation is complete.

7 Study Evaluations and Measurements

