8.3 Sample Size and Power Determination

The sample size was deemed appropriate to power the study based on previous literature in this area of research.

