9.2 Recording of Adverse Events

At each contact with the subject, the investigator will seek information on adverse events by specific questioning and, as appropriate, by examination. Information on all adverse events will be recorded immediately in the source document, and also in the appropriate adverse event module of the case report form (CRF). All clearly related signs, symptoms, and abnormal diagnostic procedures results should be recorded in the source document, though should be grouped under one diagnosis.

All adverse events occurring during the study period will be recorded. The clinical course of each event will be followed until resolution, stabilization, or until it has been determined that the study intervention or

CONFIDENTIAL

This material is the property of the University of Pennsylvania.

participation is not the cause. Serious adverse events that are still ongoing at the end of the study period will be followed up to determine the final outcome. Any serious adverse event that occurs after the study period and is considered to be possibly related to the study intervention or study participation will be recorded and reported immediately.

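### Section 6.5 closes an early leaver's participation, at odds with 6.4.1, 9.2 and 9.4.1; exit endpoint data may be lost, and 8.5 may exclude leavers' earlier data too

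*Combined protocol and SAP*

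**What the plan says.** Five places in the combined protocol and SAP bear on a subject who stops before Day 90.

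- **Section 6.4 (Subject Withdrawal)** allows withdrawal by either party: "The Investigator may also withdraw subjects who violate the study plan, or to protect the subject for reasons of safety or for administrative reasons". It asks for a record of whether each subject completes, but not of why she left.
- **Section 6.4.1 (Data Collection and Follow-up for Withdrawn Subjects)** says that subjects who withdraw consent "may be asked for one final visit or phone interview to collect any study endpoints or adverse events at that time".
- **Section 6.5 (Early Termination Visits)** covers both routes out: "If a subject decides to leave the study early or is asked by the investigator to cease participation in the study". Its operative words apply also when the subject "is asked by the investigator to cease participation in the study the subject's participation is complete". No visit or assessment follows. The schedule of procedures in section 6 has no early-termination column.
- **Section 9.2 (Recording of Adverse Events)** states: "The clinical course of each event will be followed until resolution, stabilization, or until it has been determined that the study intervention or" participation is not the cause. Section 9.4.1 makes the investigator responsible for following all SAEs until they resolve or stabilise. Neither section excepts early leavers.
- **Section 8.5 (Subject Populations for Analysis)** defines one set only, per-protocol, which requires adherence for the whole trial. Section 8.4.2 has no rule for missing endpoint readings.

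Satisfaction and volume change over 90 days are both primary (sections 3.1.4 and 8.1).

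**The concern.** Site staff facing a departing subject have two instructions. Under 6.5 they can close the file and collect nothing. Under 6.4.1 they may ask for endpoints, but only if she has withdrawn consent. A subject whom the investigator removes, for safety for example, falls outside 6.4.1, so no text says whether a last FACE-Q or Vectra reading should be taken.

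At stake is the completeness of both primary endpoints. The follow-up visits are unpaid (section 12.3) and outside standard care (section 11.4), so some loss is to be expected. If those who leave are less satisfied than those who stay, a mean taken over completers is too high. Without recorded reasons for leaving, the final report would have little basis for judging whether that happened. Appendix 15.5 asks in general terms that missing data be explained, but it does not call for the reason a subject left.

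**Working it through.** **Step 1. Set the sections side by side.**

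| How participation ends | Exit FACE-Q and Vectra | Adverse-event follow-up |
|---|---|---|
| Subject withdraws consent | 6.4.1: optional; 6.5: participation complete | 9.2 and 9.4.1: continues; 6.5: participation complete |
| Subject stops attending without withdrawing consent | No rule except 6.5 | As above |
| Investigator withdraws the subject | No rule except 6.5 | As above |

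The clash with 9.2 and 9.4.1 is the firmer one, because those sections are mandatory. The clash with 6.4.1 is softer, because that contact is optional. In the last two rows the plan is silent on endpoints, apart from the closing statement in 6.5.

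**Step 2. What data are at risk.** Readings taken before departure exist, and section 9.6 allows use of information collected before authorisation is revoked. What 6.5 puts at risk is the exit reading. A telephone contact under 6.4.1 can give FACE-Q but not a Vectra image. The earlier readings are put at risk by 8.5, not by 6.5. Injection takes place at the Day 1 visit, so whether a later leaver still counts as adherent depends on how 8.5 is read. Exclusion is possible, not certain.

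**Step 3. Inputs for size.** The plan gives N: "Total accrual will be 100 patients". Its justification is "The sample size was deemed appropriate to power the study based on previous literature in this area of research", with no SD, effect size, power or dropout rate, so the figure of 100 cannot be reproduced. The share leaving (d) and the satisfaction gap between completers and leavers (D, in SD units) are assumptions.

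**Step 4. Bias of a completer mean.** Let completers have mean m and leavers m - D. The all-treated mean is (1 - d)m + d(m - D) = m - dD. A completer-only mean is therefore too high by dD.

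- d = 0.10, D = 0.5: 0.10 × 0.5 = 0.05 SD
- d = 0.10, D = 1.0: 0.10 × 1.0 = 0.10 SD
- d = 0.20, D = 0.5: 0.20 × 0.5 = 0.10 SD
- d = 0.20, D = 1.0: 0.20 × 1.0 = 0.20 SD

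Outside that range, d = 0.05 with D = 0.25 gives about 0.01 SD, and d = 0.30 with D = 1.0 gives 0.30 SD.

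**Step 5. Compare with precision among those who remain.** The half-width is t(0.975, n - 1)/√n, in SD units.

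- n = 90: 1.987/√90 = 0.209 SD
- n = 80: 1.990/√80 = 0.223 SD

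The smallest of the four biases is 0.05/0.209, about 24% of the half-width. The largest is 0.20/0.223, about 90%. By normal approximation with SE = 1/√n, a nominal 95% interval would cover the all-treated mean 92.4% of the time in the first case (d = 0.10, D = 0.5) and 56.8% in the second (d = 0.20, D = 1.0).

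**The case against.** The strongest reply is that this is a wording problem with little consequence. Section 6.5 says participation is complete; it does not say in words that data collection ends. It can be read with 6.4.1 as meaning that scheduled visits stop and one optional contact remains. Sections 9.2 and 9.4.1 apply to leavers as they stand. Both inputs to the bias are assumed, and satisfied patients may also skip visits because they need nothing further. Dissatisfied patients have a reason to return: section 6.3 provides for unscheduled visits and section 11.1 mentions filler removal.

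Much of this stands, and it rules out three stronger readings that a reader might infer.

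- *Dissatisfied leavers drop out of the primary endpoint because of 6.5.* The documents do not say who leaves or why, and 6.5 discards no earlier reading. Whole-patient exclusion would come from 8.5.
- *Leavers' safety data are removed.* Sections 9.2 and 9.4.1 still require follow-up; the defect is that 6.5 appears to contradict them.
- *The bias can equal the whole confidence half-width.* That sets a 20% loss against the half-width for the full 100. With 80 completers the half-width is 0.223 SD, which exceeds 0.20 SD. The formula also gives leavers no weight, so an analysis using their earlier visits could be less affected.

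The reply does not supply a rule for exit endpoints after investigator withdrawal, and it does not remove the need to choose between two readings of 6.5.

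**Conclusion.** The inconsistency is established from the text alone: 6.5 does not fit with 6.4.1, 9.2 and 9.4.1, and exit endpoint collection is undefined for subjects the investigator withdraws. Loss of FACE-Q and Vectra data from the point of leaving is a real possibility, and 8.5 may extend the loss to earlier readings.

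The effect on the satisfaction result is conditional. It requires that leaving be related to dissatisfaction, which is plausible but not stated, and that the analysis be confined to completers. Under the assumed 10-20% leaving and 0.5-1.0 SD gap, the overstatement is below the half-width throughout, but at the upper end it is large enough to spoil interval coverage. The case for acting rests on the low cost of the change, not on a demonstrated bias.

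**What to change.** 1. Reconcile 6.5 with 6.4.1, 9.2 and 9.4.1. State one data-collection rule for every early leaver who agrees, whether she or the investigator ends participation: she is asked for one exit contact. In clinic this gives FACE-Q and Vectra. If she will not attend, FACE-Q is taken by telephone and the volume reading is recorded as missing.
2. Record the reason for leaving alongside the completion status that 6.4 already requires.
3. Say in 6.5 that ending participation does not end the adverse-event follow-up under 9.2 and 9.4.1.
4. Amend 8.5 so that the primary analysis uses all treated subjects with all available readings, including exit readings at their actual day. Without this step the readings gained in step 1 could still be left out.

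The cost is a short amendment and one visit or call per early leaver, a contact that 6.4.1 already permits for those who withdraw consent. At 10-20% leaving that is 10 to 20 contacts among 100 subjects.
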